9.6 Scheduling Intervention Visits

There are three requirements for scheduling of intervention visits:

1. The first intervention visit should occur on Day 7 or earlier, where the day of randomization = Day 0.
2. The schedule of intervention visits is anchored to the date of randomization regardless of when the intervention starts.
3. Intervention visits should never occur on two consecutive days, even when moving from one week to the next.

For all randomized participants, Week 1 will begin on the day of the first intervention visit or on Day 7 post-randomization, whichever is earlier. Subsequent weeks will start on the same day of the week as Week 1. For example, if the participant's first intervention visit is on a Wednesday, each intervention week for that participant will extend from Wednesday to Tuesday (inclusively). Alternatively, if the first visit has not yet occurred by Day 7 and Day 7 is a Monday, then the participant's intervention weeks will extend from Monday to Sunday (inclusively).

In certain circumstances (e.g., illness, travel), the first intervention visit may be scheduled after Day 7.

Ideally participants will receive 2 visits per week for 16 weeks post-randomization (32 visits total). However, missed visits in a given week can be replaced by makeup visits in subsequent weeks (not to exceed 3 visits in any given week) as long as the visits are on non-consecutive days. If the participant has not had 32 visits by the end of 16 weeks, makeup visits can be performed during the subsequent two weeks to get as close as possible to the target of 32 visits.

Section 10: Study Measures

A list of study measures is provided below. All of the measures will be interview-based or based on observations of performance or physiological assessments. No proxy data will be allowed at baseline. However, at the 16-week follow-up visit, a proxy may be contacted to provide information about the participant's walking ability. This information will be used as part of the adjudication process, as described in section 11.5. Also, the four-week phone calls will be conducted with a proxy when the participant is not available.

In the description of measures below, we identify the measures that will not be collected for participants consented under protocol version 11.0 or later.

10.1 Screening Evaluations

There will be three primary components to the screening process: the chart review in the acute care setting (phase 1), the phase 2 screen, and screening for final eligibility (phase 3) that includes calculated BMI, the 3MS, and the SMWT. These components will be typically administered over three contacts, in-person or by telephone (phase 2). Those who qualify after phases 1 and 2 will be invited for the first clinic visit for phase 3 screening (see section 7.5).

10.1.1 Weight, Height, and BMI

Height (in feet and inches) will be measured once at the baseline visit using a standard stadiometer. Weight (in pounds) will be measured using a digital scale at baseline and at each follow-up visit. Measured height and weight will be used to calculate BMI.

10.1.2 Modified Mini-Mental State Examination (3MS)

The 3MS is a test of global cognitive function which assesses a broad variety of cognitive dimensions and is an expanded 100 point version of the original Folstein Mini-Mental State Exam.^{153,154} The 3MS will be used at the baseline visit to identify and exclude participants with cognitive impairment (3MS score <73).¹⁵⁵

10.2 Primary Outcome Measure: Community Ambulation

The primary study outcome reflects the concept of a minimum distance a person needs to be able to walk to carry out usual activities in the community. This will be defined as achieving the threshold value of 300 meters or more on the SMWT.

Performance of the SMWT at the baseline assessment also will be used to define final eligibility prior to the collection of additional baseline data. Participants who walk less than four meters in 40 seconds (<0.1 m/sec) or who walk 300 meters or more in six minutes will be excluded from the trial. Participants with angina, extreme shortness of breath, or ambulating with severe pain during the SMWT also will be excluded.

Participants will be asked to walk back and forth on a measured path marked clearly at both ends for turning purposes, while being told when each minute has passed, and receiving verbal encouragement ("you're doing well" or "keep up the good work") every 60 seconds. Test-retest reliability in older adults is excellent ($r = .95$).¹⁰⁷ Concurrent validity with $\dot{V}O_2$ peak ($r = .64$) and cycle ergometry ($r = .58$) have been reported.^{105,156,157}

10.3 Secondary Outcome Measures - Precursors to Community Ambulation

10.3.1 Endurance

To assess endurance, the SMWT (described above) will be used to obtain a continuous measure of total distance walked in six minutes.¹⁵⁸ The SMWT is highly correlated with workloads, heart rate, oxygen saturation, and dyspnea responses when compared to bicycle ergometry and treadmill exercise tests in older persons.^{105,156,158} It has been performed by elderly, frail and severely compromised participants who cannot perform standard maximal treadmill or cycle ergometry exercise tests.^{31,159}

10.3.2 Balance

We will use an enhanced balance measure that includes the balance subscale of the Short Physical Performance Battery (SPPB) and two additional single leg stands (eyes open and eyes closed), as used in the National Health and Aging Trends Study (NHATS).¹⁶⁰ For the test of standing balance, participants are asked to maintain balance in three positions, characterized by a progressive narrowing of the base support: with feet together (side-by-side position), the heel of one foot beside the big toe of the other foot (semi-tandem position), and the heel of one foot in front of and touching the toes of the other foot (tandem position). For each of the three positions, participants are timed to a maximum of 10 seconds. Participants are then asked to stand on one leg (on the side of the fracture) with eyes open and again with eyes closed. Each of the single leg stands are held for up to 30 seconds. The number of seconds is then summed across the 5 items to obtain the measure of balance. These tests are hierarchical such that when a participant fails an item, the harder ones are not administered and receive a score of 0.

10.3.3 Quadriceps Muscle Strength

Isometric force for bilateral knee extensors will be measured with a portable, hand-held dynamometer (Microfet2 Manual Muscle Tester). Participants will be seated on the strength testing chair, with hip flexion 90° and knee flexed to 70°, stabilization straps on the pelvis and thigh, and resistance applied just proximal to the ankle on the anterior surface of the leg.¹⁶¹ Participants will be asked to push as hard and as fast as possible for five seconds. Three maximal effort trials, with a one-minute rest between trials, will be performed. The reported test-retest reliability with hand-held dynamometry is excellent ($r > .90$) if tested in one session and in subjects with muscle weakness (intraclass correlation coefficient $\geq .90$).¹⁶²⁻¹⁶⁴ The peak force will be recorded for each of the three trials and the highest value will be used.

This measure will not be collected for participants consented under protocol version 11.0 or later.

10.3.4 Lower Extremity Function

A modified version of the Physical Performance Test (mPPT)¹⁶⁵ will be used to measure lower extremity function at baseline and follow-up. The modification, used by Binder et al., substitutes a chair-rise task and a balance task for writing and eating tasks, in order to emphasize lower extremity function.⁶⁸ The modified PPT includes nine standardized tasks that will be timed (e.g., picking up a penny from the floor, standing up five times from a 16-inch chair). The tasks are performed twice and the times from the two trials are averaged. The score for each item ranges from 0 to 4, with 36 representing a perfect score. Test-retest reliability for the modified PPT score is 0.96.²² Because there is some overlap between the mPPT and SPPB items, we have integrated the two scales so that participant burden is minimized but it is still possible to obtain scores on each of the scales.

10.3.5 Fast Walking Speed

Within the mPPT, participants are asked to walk a distance of 50 feet walking quickly but safely. The time required to walk 50 ft will be the measure of fast walking speed.

10.3.6 Cost Effectiveness: Health Care Utilization

Resource utilization will be tracked every four weeks via telephone interview and unit costs will be assigned to each resource for which data are obtained. Resource use will reflect health care use (including both formal and informal care) since the last telephone interview. This interview will be patterned after that used in the NIH-sponsored Spine Patient Outcomes Research Trial (SPORT).¹⁶⁶ In addition to caregiver costs, the questionnaire will document other resource use including hospitalizations, other care facilities, health care visits, and diagnostic tests. As in SPORT, a health diary will be provided to each participant to assist them in accurately recording health care encounters and use of health services.

Effectiveness will be assessed in the QALY framework where health state values will be used to reflect the desirability for health outcomes on a scale from 0 (worst imaginable health state) to 1 (best imaginable health state). To estimate QALYs, health state values will be obtained using the SF-6D health state classification system,¹⁶⁷ which defines health states using participant responses to the SF-36 (described below). QALYs estimated using SF-6D are consistent with recommendations to use societal values in economic evaluations in health and medicine.¹³⁶ Although current SF-6D scoring uses preference weights from a UK population, use of the SF-6D will facilitate the planned model-based comparison between trial interventions and usual care, because several BHS investigations have utilized SF-36 in similar hip fracture populations.

Costs associated with participant-reported resource utilization will be estimated using the Resource-Based Relative Value Scale (RBRVS)¹⁶⁸⁻¹⁷⁰, which is used by the Center for Medicare and Medicaid Services (CMS) to reimburse physicians for their services. This approach has the advantage of reflecting national fee schedules and relating them to the RBRVS. To estimate costs of other health care services not consistently covered by Medicare, providers will be surveyed on charges for services at the geographic locations involved in this study. For each item, units of utilization will be multiplied by prevailing charges to estimate costs for each participant. To estimate indirect costs, information about informal caregivers' employment status and job class will be obtained at baseline. This will allow for estimation of the indirect economic costs associated with informal caregiving. Costs associated with providing the interventions will be estimated based on the amount of physical therapist time required to deliver the interventions as recorded during the trial.

This measure will not be collected for participants consented under protocol version 11.0 or later.

10.4 Tertiary Outcomes

A series of outcomes that are relevant for the recovering hip fracture participant also will be evaluated. These were selected since: 1) all are affected by a hip fracture; and 2) all are important in understanding the degree to which hip fracture patients recover.

10.4.1 Activities of Daily Living (ADLs)

We will measure ADLs using the Pepper Assessment Tool for Disability (PAT-D)^{171,172} with two modifications. First, two items (walking a quarter mile and walking across a small room) were added to address perceived gaps in the original PAT-D scale. This modification is consistent with the version used in the Lifestyle Interventions and Independence for Elders study.¹⁷³ Second, two items (walking several blocks and lifting heavy objects) were deleted to avoid

duplication with other items in the scale. The resulting 19-item scale allows examination of three subscales (basic ADL, functional limitations, and instrumental ADL).

This measure will not be collected for participants consented under protocol version 11.0 or later.

10.4.2 Quality of Life (SF-36)

We will use an interviewer-administered version of the SF-36, a health survey that assesses quality of life in eight subscales (physical function, social function, role-physical, role-emotional, bodily pain, mental health, general health, and vitality).¹⁷⁴ The measure has been validated as a generic measure of quality of life in many different populations, including patient and non-patient samples.^{174, 68,175,176}

This measure will not be collected for participants consented under protocol version 11.0 or later.

10.4.3 Balance Confidence

The Activities-specific Balance Confidence (ABC) scale¹⁷⁷ is a 16-item measure that asks respondents to rate their confidence in maintaining their balance while doing daily activities. Test-retest reliability, internal consistency, and concurrent validity with fall and physical activity are high.^{177,178} This measure has been used successfully in hip fracture patients.^{32,179}

This measure will not be collected for participants consented under protocol version 11.0 or later.

10.4.4 Yale Physical Activity Survey (YPAS)

This interviewer-administered questionnaire includes five categories of common activities related to work, exercise, and recreation performed during a typical week in the past month.¹⁸⁰ The YPAS increases the sensitivity of other physical activity surveys by describing a wider range of lower intensity activities that older adults often engage in. Participation in each activity (hrs/week) will be multiplied by an intensity code (kcal/min) and then summed over all activities to calculate a weekly energy expenditure summary. The measure has been validated against several physiological variables of habitual activity.^{180,181} The YPAS has been used to estimate change in older adults in an exercise intervention program.¹⁸²

This measure will not be collected for participants consented under protocol version 11.0 or later.

10.4.5 Improvement in Walking

Whether or not there was an increase of at least 50 meters in the distance walked on the SMWT will be assessed as a tertiary outcome. This distance has been shown to be clinically meaningful.^{183,184}

10.4.6 Short Physical Performance Battery (SPPB)

The SPPB evaluates lower extremity performance in older persons based on timed short distance walk, repeated chair stands, and a set of balance tests.¹⁸⁴⁻¹⁸⁶ Each of the tasks is assigned a score ranging from 0 to 4, with 4 indicating the highest level of performance and 0 an inability to complete the test. The test takes about 10-15 minutes to administer and was designed to be administered by a lay interviewer in a setting with limited space. The battery has an excellent safety record. It has been administered to well over 10,000 persons in various studies and no serious injuries are known to have occurred. The SPPB components and total

score are derived from normative values obtained from a population-based study.^{184,186} The total score ranges from 0 to 12; there are three subscales embedded in the SPPB.

Standing balance. For the test of standing balance, participants are asked to maintain balance in three positions, characterized by a progressive narrowing of the base support:, with feet together (side-by-side position), the heel of one foot beside the big toe of the other foot (semi-tandem position), and the heel of one foot in front of and touching the toes of the other foot (tandem position). For each of the three positions, participants are timed to a maximum of 10 seconds.

Walking speed. Walking speed is assessed by asking participants to walk at their usual pace over a 4 m course. Participants are instructed to stand with both feet touching the starting line and to start walking after a specific verbal command. Participants are allowed to use walking aids (cane, walker, or other walking aid) if necessary, but not the assistance of another person. Timing begins as soon as the participant starts to walk and the time in seconds needed to complete the entire distance is recorded. The faster of two walks is used to compute walking speed.

Chair stands. The repeated chair stands test is performed using a straight-backed chair, which is placed with its back against a wall. Participants are first asked to stand once from a sitting position with their arms folded across their chest. If they are able to perform the task, they are then asked to stand up and sit down five times, as quickly as possible. The time to complete the task is recorded.

10.4.7 Depressive Symptoms

Depressive symptoms will be measured using the 20-item Center for Epidemiologic Studies Depression (CES-D) scale,¹⁸⁷ which asks about depressive symptoms experienced in the previous week. There is evidence that recovery post-fracture is delayed in the presence of depression.¹⁸⁸⁻¹⁹¹ This scale ranges from 0-60 with higher scores indicating greater depression.

10.4.8 Cognitive Status

Cognitive status will be assessed at follow-up using the 3MS (see section 10.1.2).

This measure will not be collected for participants consented under protocol version 11.0 or later.

10.4.9 Nutritional Status

Nutritional status will be assessed using the Mini Nutritional Assessment-Short Form (MNA®-SF),^{6,192} a validated and widely used malnutrition screening tool.¹⁹²⁻¹⁹⁵ We are using a modified version of the MNA®, approved by the scale's developer (the Nestlé company), to facilitate use as an interviewer-administered tool in a research setting. Scores range from 0 to 14; participants scoring ≤7 will be considered malnourished; those scoring 8-11 will be considered to be at risk of malnutrition; and those scoring 12-14 will be considered to have normal nutritional status.^{6,192}

This measure will not be collected at follow-up for participants consented under protocol version 12.0 or later.

10.5 Clinical and Background Characteristics

Information on a small number of other patient characteristics will be collected to allow description of the study population, to allow analyses of differential effects in subgroups (i.e.,

effect modification), and to help in the interpretation of results.

10.5.1 Demographic and Surgical Characteristics

For descriptive purposes, information on the following participant characteristics will be collected either during screening or at the baseline assessment: age, gender, race, living situation, marital status, educational level, fracture type, and surgery type.

10.5.2 Functional Comorbidity Index

The Functional Comorbidity Index (FCI) is a clinically based measure developed by Groll *et al.* This index includes a checklist of 18 comorbid conditions scored 1 or 0. A maximum score of 18 indicates the highest number of comorbid illnesses. The FCI was specifically developed to predict physical functioning.¹⁹⁶

10.5.3 Psychological Measures

The following psychological measures will be administered at the baseline assessment to allow us to perform pre-specified subgroup analyses.

Life Orientation Test-Revised (LOT-R)

The LOT-R assesses self-reported optimism and pessimism. A total of six brief statements is read to the participant, and response categories range from strongly disagree to strongly agree on a 5-point Likert type scale; three items measure optimism and three items measure pessimism.¹⁹⁷

Brief Resilience Scale

The Brief Resilience Scale assesses self-reported ability to bounce back after a stressful event. A total of six brief statements is read, and response categories range from strongly disagree to strongly agree on a 5-point Likert-type scale.¹⁹⁸

10.6 Other Measures to be Monitored

10.6.1 Adherence

Adherence with PT interventions. PTs will submit a visit form for each of the 32 visits that records date of visit; start and end time of the visit; reason for missed visit; what activities were performed; and whether activities were performed as prescribed. For the PUSH group, we will also obtain information about the intensity of each activity at initiation of the intervention and every four weeks during the intervention period. Logs completed by PTs will record the detail of each designated activity during intervention sessions as well as any precautions or modifications to activities. Reasons for protocol variations will be noted in the PT log books.

Additionally, at the end of each intervention visit, the PT will retrieve the average HRs for laps 2 and 3 from the Polar heart rate monitor receiver and record them in the logbook and on the appropriate data forms. The Polar heart rate monitoring will provide a dichotomous variable reflecting whether, during laps 2 and 3 of each intervention session, the participant's average HR was equal to or greater than his or her target heart rate (± 5 beats). In addition, the IM will perform ongoing qualitative reviews of the HR curves to ensure that the pattern of activity is consistent with pre-specified criteria established for each intervention.

Adherence with study vitamins/supplements. Vitamin D, calcium, and multivitamin adherence will be monitored by pill counts every four weeks during the intervention period and by self-report during the 4-week telephone calls for the entire 16-week study period.

In protocol version 11.0, we will eliminate the collection of information on use of study-provided dietary supplements. However, procedures for drug accountability will remain unchanged (see section 3.2.3).

10.6.2 Weight Loss

Weight will be monitored by the PTs every four weeks during the 16-week intervention period using a standard digital scale.

10.6.3 Reportable Adverse Events (RAEs)

Reportable adverse events (RAEs), which include serious adverse events (SAEs), unexpected AEs or injury that occurs under supervision by study staff, will also be obtained during the study. These events will be tracked in a separate database by the CCC. RAEs will be captured every four weeks during the telephone interviews using standardized questions on the Reportable Adverse Events Form. Participants (or their proxies) will be asked about life-threatening or significant medical events and the outcomes of these events. RAEs will also be asked about by study staff prior to each PT visit and clinical site follow-up assessment. RAEs may be spontaneously reported to any study staff member throughout the study (see section 13.4.1).

10.6.4 Expected Adverse Events (AEs)

Expected AEs will be assessed every four weeks during the telephone interview. Participants (or their proxies) will be asked a series of standardized questions related to pain (feet, hip, back, knees); breathing problems or chest pain; skin irritations, rash, or skin tears; numbness or tingling; and falls (with and without injury).

Section 11: Study Procedures

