12.1.3 Safety Considerations for the PUSH Intervention

There is no expectation that the PUSH intervention will evoke serious cardiovascular responses; however, participants will be warned of a possible risk. Cardiac events are rare, with estimates of one event per 60,000 participant-hours in aerobic exercise programs.²⁰⁰ No significant cardiac events were reported after performing 1-RM testing for over 6600 healthy subjects.²⁰¹ The American Heart Association's guidelines for resistance training for adults with and without cardiovascular disease reports the safety of high intensity resistance training and testing in persons with coronary disease which found an absence of anginal symptoms, ischemic ST-segment depression, abnormal hemodynamics, complex ventricular dysrhythmias, and cardiovascular complications.^{202,203} Less serious risks may include chest pain, fainting, hypotension, or muscle strain. We have minimized risk to participants by following the guidelines suggested by Gill et al.¹⁹⁹ Blood pressure and heart rate will be monitored using a standard blood pressure cuff and palpation of peripheral pulse.

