Another concern is the presence of osteoporosis and the risk of inducing a compression fracture or a lower extremity fracture. The exercises have been designed to minimize this risk. The risk of inducing a compression fracture will be minimized because the exercises are performed in supine and upright standing positions with minimal to no trunk flexion.²⁰⁴ The PT will also remind the participant to minimize flexion to the spine during all standing exercises. Using an exercise device that eliminates the risk of weights falling on a person, and using only voluntary muscle contractions during isometric testing, will reduce the risk of lower extremity fracture. We do not anticipate additional risk for the PUSH intervention for the following reasons: 1) by 12 weeks post-fracture, there is moderate stability from the bone callus formation, 2) participants will only be included if they have medical clearance to participate in full weight bearing activities, and 3) the device limit is 100 pounds (which in most cases is less than body weight) resulting in less load than walking up and down stairs. Delayed onset muscle soreness is a common occurrence after the initiation of an exercise program. The soreness occurs in the muscle belly 1-3 days after the initiation of exercise and lasts 2-3 days. There is no effective way to eliminate the risk of delayed onset muscle soreness, but it is hoped that the orientation process and gradual increase in intensity will reduce the risk. The participants will be informed about the condition, what it feels like, how long it lasts, and suggested ways of decreasing the pain including the use of superficial heat or ice. If a participant reports continued discomfort, the study clinician will discuss this with the participant and contact their primary care provider (PCP) as necessary. Please see Table 3 below for a summary of alerts and appropriate action during the PT intervention visits.

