12.1.7 Safety Considerations for the Nutritional Intervention

Individuals who have sustained a hip fracture are frequently at risk for protein and calorie malnutrition and have low calcium and vitamin D intake.²⁰⁵ Individuals enrolled in the study will be screened with the MNA®-SF and if their scores indicate that they are malnourished, they will receive in-person nutritional counseling by a registered dietician. Individuals enrolled that have a serum albumin value 2.5-3.5 will also receive in-person nutritional counseling by a registered dietician, regardless of score on the MNA®-SF. Participants who are at risk or not at risk for malnutrition will receive a telephone consultation from the dietician on maintaining proper diet. The RD will schedule an in-person visit for those at risk if he/she feels it is necessary based on the telephone consultation. All subjects will receive vitamin D, calcium, and multivitamin supplementation for the 16-week study period, all of which represent best practices for this disabled group of participants. There are small risks associated with vitamin D, calcium, and multivitamins including gastrointestinal complaints (including mild constipation or diarrhea, stomach upset) and kidney stones. Those with a calculated creatinine clearance <30 ml/min, elevated total or ionized calcium, or history of kidney stones, primary hyperparathyroidism, or sarcoidosis will not receive calcium supplements. A participant who experiences an episode of kidney stones during the study period will stop receiving calcium supplements.

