13.2.2 Expectedness

AEs will be assessed as to whether they were expected or unexpected based on current knowledge. Categories are:

Expected: An AE that is anticipated on the basis of prior experience with the intervention under investigation; an event that can be attributed to the underlying condition of the participant being studied; or an event that can be attributed to the patient population being studied (see section 13.3). Expected AEs are captured in a standardized way by blinded personnel.

Unexpected: An AE that was not anticipated on the basis of prior experience with the intervention under investigation; an event that cannot be attributed to the underlying condition of the participant being studied or to the patient population; or an expected event whose frequency or severity exceeds what was anticipated (see section 13.4.2). Unexpected AEs are reportable.

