13.3 Expected AEs

Expected AEs will be captured through telephone interviews every four weeks by blinded personnel, using the Expected Adverse Events Form. Following are expected adverse events that have been listed in the ICF:

- foot pain
- hip pain
- back pain
- knee pain
- breathing problems
- chest pain or discomfort
- skin tears, rash, or skin irritations
- numbness or tingling
- fall (with or without injury)

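### The blinded four-weekly adverse event questions match the TENS risks but have no item for four of five named lesser PUSH effects or for either supplement risk

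*Protocol*

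**What the plan says.** Protocol 13.2.2 treats an event as expected if it is anticipated from experience with the intervention, or attributable to the participant's condition or the population. It states: "Expected AEs are captured in a standardized way by blinded personnel". The instrument is the four-weekly telephone form. Under 10.6.4, participants or proxies are "asked a series of standardized questions related to pain (feet, hip, back, knees); breathing problems or chest pain", and then about skin problems, numbness or tingling, and falls. Section 13.3 gives the same content under the lead-in "Following are expected adverse events that have been listed in the ICF", including "skin tears, rash, or skin irritations".

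The anticipated risks are named in 12.1:

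- **PUSH (12.1.3):** "Less serious risks may include chest pain, fainting, hypotension, or muscle strain". The section adds: "Delayed onset muscle soreness is a common occurrence after the initiation of an exercise program".
- **PULSE (12.1.5):** skin burn or irritation, reaction to adhesive, skin tears, and tingling or numbness while current flows.
- **Supplements (12.1.7):** gastrointestinal complaints and kidney stones, with a rule: "A participant who experiences an episode of kidney stones during the study period will stop receiving calcium supplements".

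Under 13.8 the DSMB reviews tabulated non-serious and expected events twice a year. Neither protocol Section 15 nor the SAP specifies a between-arm adverse event analysis, so that tabulation is the main stated use of these data.

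**The concern.** The solicited list should follow from the risks the protocol anticipates. For PULSE it does; for PUSH it mostly does not. Protocol 9.4 describes tingling as the sensation TENS is set to produce, and the form asks about it. Delayed soreness, which 12.1.3 calls common, has no item, and the pain sites (feet, hip, back, knees) leave out thigh, calf and buttock.

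At stake is how even-handed the only blinded, structured source of non-serious events is, in a trial comparing a high-intensity with a low-intensity programme. A second, separate matter is that the calcium rule in 12.1.7 depends on learning of a kidney stone, and no passage says how that would happen.

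**Working it through.** The plan gives no figure to reproduce. The check matches each named risk to the solicited items, then traces the other routes by which an unmatched event could be recorded.

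**Step 1. Named risks against the list in 10.6.4 and 13.3**

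| Source | Named risk | Item on the list? |
|---|---|---|
| PULSE, 12.1.5 | Skin burn or irritation | Yes (burn only by implication) |
| PULSE, 12.1.5 | Adhesive reaction | Yes (rash or irritation) |
| PULSE, 12.1.5 | Skin tears | Yes |
| PULSE, 12.1.5 | Tingling or numbness | Yes |
| PUSH, 12.1.3 | Chest pain | Yes |
| PUSH, 12.1.3 | Fainting | No |
| PUSH, 12.1.3 | Hypotension | No |
| PUSH, 12.1.3 | Muscle strain | No |
| PUSH, 12.1.3 | Delayed muscle soreness | No |
| Supplements, 12.1.7 | Gastrointestinal complaints | No |
| Supplements, 12.1.7 | Kidney stones | No |

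The count is PULSE 4 of 4, PUSH 1 of 5, supplements 0 of 2.

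**Step 2. Other routes for the unmatched PUSH effects**

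- *Supervised injury (13.4.3).* Any injury under study supervision is reportable, whatever its severity. A strain during a session is therefore captured. Soreness is not reached in the same way: 12.1.3 places it 1 to 3 days after exercise starts. By the end of week 8, PUSH participants are also told to walk independently once or twice a week (9.3), and that is unsupervised.
- *Unexpected event (13.4.2).* An uncommon event absent from the consent form and 13.3 can qualify and, if potentially related, goes on an Incident Report. To be reportable it must also suggest more risk than was previously known, which an effect already named in 12.1.3 would ordinarily fail to do.
- *General RAE questions (10.6.3).* These ask about life-threatening or significant medical events. Ordinary soreness does not fit.
- *Therapist monitoring (12.1.4, 12.1.6, Table 3).* In both arms therapists check blood pressure three times per session and watch for strain, dizziness and hypotension. Therapists are unblinded (6.4), and no passage sends these observations to the expected-event tabulation.
- *Neighbouring items.* Hip pain, knee pain and fall questions may pick up some strain, soreness or fainting, but not under those names.

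What remains without blinded standardized capture is soreness or strain that is delayed or unsupervised, and dizziness outside sessions.

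**Step 3. Kidney stones**

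RAEs are asked about at 4 calls, up to 32 therapist visits and 1 follow-up visit: 4 + 32 + 1 = up to 37 scheduled contacts in 16 weeks. No specific kidney-stone question is described for any of them. A stone needing hospitalization is an SAE (13.4.1). One managed without admission is not on the expected list and need not be serious. Version 11.0 dropped the Health Care Utilization questionnaire from the calls (11.3), which removed an indirect route.

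**Step 4. Which gap differs by arm**

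Supplements go to all participants regardless of group (Section 1, 9.2). The supplement gap therefore affects both arms alike. Any imbalance between arms rests on the PUSH effects alone.

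**The case against.** The strongest reply is that these events are watched. The therapist monitoring in 12.1.4 and 12.1.6 is worded alike for both arms, every session opens with health questions (9.5.3), and supervised injuries are reportable without any threshold. Seven of the nine items in 13.3 (four pain sites, breathing, chest pain, falls) are not specific to TENS and bear on exercise load. The DSMB approves the expected-event list (13.1). People with a history of kidney stones are not given calcium (3.2.3, 12.1.7). Delayed soreness lasts only 2 to 3 days, so a four-weekly call suits it poorly.

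Much of this stands, and it rules out several stronger readings that a reader might infer:

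- *That the missing events never reach the data.* Supervised injuries and Incident Reports are real routes.
- *That the calcium rule has no scheduled trigger at all.* General RAE questions come at every call and before every therapist visit. What is missing is a specific question and a stated link to the rule.
- *That the supplement omissions tilt the arm comparison.* Both arms receive the supplements.
- *That PUSH is shown to look safer than it is.* The documents give no event rates, and 13.8 does not limit the DSMB's table to the solicited items. Only a tendency can be inferred.

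The reply does not supply what 13.2.2 promises, which is standardized capture by blinded staff. Session monitoring by unblinded therapists is safety management. DSMB approval of the list does not reconcile it with 12.1.3. Recall over four weeks is imperfect, but it is already accepted for falls and skin tears, and 11.3 provides a health diary to help.

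**Conclusion.** The concern holds in a limited form. The solicited list covers all four TENS-type risks, one of five less serious PUSH effects and neither supplement risk. Delayed or unsupervised soreness and strain, and dizziness outside sessions, lack blinded standardized capture, so the expected-event tables would tend to under-count PUSH-type effects. The size of the under-count cannot be given, because no event rates are stated. Separately and equally in both arms, gastrointestinal complaints and kidney stones have no specific scheduled question, and a stone managed without admission could be missed.

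This rests on 10.6.4 and 13.3 describing the form fully. The Expected AE Form, RAE Form, consent form and Manual of Procedures are not among the documents; if the form already carries these items, the point reduces to correcting the protocol text. The change is worth making because it is cheap, but it does not affect the primary analysis.

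**What to change.** Reconcile 10.6.4 and 13.3 with 12.1.3 and 12.1.7 by adding four yes/no items to the four-weekly form, asked identically in both arms: muscle soreness or strain; dizziness or fainting; stomach or bowel upset; kidney stones. Hypotension itself cannot be asked about by telephone; the dizziness item covers its symptoms, and session readings continue. Have a yes on kidney stones notified to the site clinician, so that the rule already in 12.1.7 can be applied as written; no clinical rule changes. Tabulate the new items by arm for the DSMB and state the date they were added, so that calls before and after are not pooled as if asked alike.

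The cost is a form and web-entry update and about one extra minute per existing call. The main drawback is coverage. Protocol 15.6.2 expects about 160 of 210 participants under the procedures before version 11.0, so at most about 210 − 160 = 50 later participants, plus those still being called, would be asked the new items.
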